**BY: - [name]**

**DECEMBER, 2022**

**NEKEMTE,ETHIOPIA**

## Background

Malaria is a life-threatening disease caused by a parasite called Plasmodium. It is transmitted to humans through the bite of infected female Anopheles mosquitoes. Once inside the human body, the parasites multiply in the liver and then infect red blood cells, leading to destruction of the cells and the release of more parasites into the bloodstream.

The symptoms of malaria include fever, headache, chills, and flu-like symptoms such as sweating, muscle aches, and fatigue. In severe cases, malaria can cause organ failure, seizures, coma, and death.

Malaria is a major health problem in many parts of the world, particularly in sub-Saharan Africa, where it is a leading cause of death among children under the age of five. However, it is preventable and treatable with the use of antimalarial drugs, insecticide-treated bed nets, and indoor spraying of insecticides.

Efforts to control and eliminate malaria have been ongoing for many years, with the goal of reducing the burden of the disease and ultimately eradicating it. These efforts include the development of new drugs and vaccines, as well as the implementation of prevention and control measures in affected areas.

Uncomplicated malaria is a type of malaria that is not severe and has not yet affected vital organs like the brain or kidneys. It is caused by the Plasmodium parasite and is transmitted through the bite of infected mosquitoes.

Plasmodium Vivax is a type of malaria parasite that causes uncomplicated malaria, which can be treated with anti-malaria drugs such as Chloroquine and Primaquine. However, there have been concerns about the emergence of drug-resistant strains of Plasmodium Vivax, which has led to the need for studies on the therapeutic efficacy of these drugs. Several clinical trials have been conducted to evaluate the effectiveness of Chloroquine and Primaquine in combination for treating uncomplicated Plasmodium Vivax malaria. These studies have shown that the combination therapy is highly effective in clearing the parasites from the blood and preventing

relapses. However, the optimal dosages and duration of treatment for this combination therapy are still being investigated to improve its therapeutic efficacy.

The treatment of uncomplicated malaria involves the use of antimalarial drugs such as Chloroquine, Artemisinin-based Combination Therapy (ACT), and Quinine-based regimens. The choice of drug and treatment regimen depends on the species of the malaria parasite, the severity of the infection, and the patient's age and weight.

Antimalarial drugs work by killing the parasites in the blood and preventing them from multiplying. They are usually administered orally, and the duration of treatment varies depending on the drug used and the severity of the infection.

In addition to drug treatment, supportive care such as hydration and management of symptoms like fever, headache, and nausea is also important in the treatment of uncomplicated malaria. Regular monitoring of patients is also necessary to ensure the effectiveness of treatment and detect any complications that may arise.

Monitoring the therapeutic efficacy of antimalarial drugs is crucial for ensuring effective treatment of uncomplicated malaria. It involves the regular evaluation of the clinical and parasitological response of patients to the drugs. This is done through clinical examination, laboratory tests, and follow-up visits to assess the patient's symptoms and the presence of malaria parasites in the blood.

The World Health Organization (WHO) has developed standardized protocols for monitoring the therapeutic efficacy of antimalarial drugs, which involve conducting clinical trials to evaluate the effectiveness of the drugs in different regions. These trials include evaluating the parasite clearance rate, the fever clearance time, and the rate of treatment failure.

Regular monitoring of therapeutic efficacy is essential in detecting the emergence of drug-resistant strains of malaria parasites and improving treatment regimens to ensure effective treatment and prevent the spread of drug resistance.

## Statement of the Problem

Antimalarial drug resistance is a major barrier to the control and elimination of malaria. The emergence of drug-resistant strains of *Plasmodium* parasites has significantly impacted the effectiveness of antimalarial drugs in treating and preventing malaria.

The burden of antimalarial drug resistance is particularly high in sub-Saharan Africa, where the majority of malaria deaths occur. Resistance to Chloroquine, once the most widely used antimalarial drug, is now widespread in many parts of Africa and other regions. Resistance to other drugs such as Sulphadoxine-pyrimethamine, Amodiaquine, and Artemisinin-based Combination Therapy (ACT) has also been reported in some regions.

The emergence of drug resistance has increased the cost of malaria treatment and prevention, as alternative drugs and combination therapies must be used. It also poses a challenge to malaria control efforts, as it reduces the effectiveness of interventions such as insecticide-treated bed nets and indoor residual spraying.

Efforts to combat antimalarial drug resistance include the development of new drugs and combination therapies, as well as the strengthening of surveillance and monitoring systems to detect and respond to drug resistance.

Despite the widespread use of Chloroquine and Primaquine in combination for the treatment of uncomplicated *Plasmodium Vivax* malaria, there is still a need to investigate the optimal dosages and duration of treatment to improve therapeutic efficacy. The emergence of drug-resistant strains of *Plasmodium Vivax* also poses a challenge to the effectiveness of this combination therapy. Therefore, there is a need to conduct further studies to evaluate the therapeutic efficacy of Chloroquine and Primaquine in combination and to monitor the emergence of drug-resistant strains to improve the management of uncomplicated *Plasmodium Vivax* malaria.

## METHODS

### Study Area and Period

The study will be carried out from December, 2022 to March, 2023 in Shecha Health Center, Arbaminch Town, South West Ethiopia, 2022/23. Shecha Health Center is found in Arbaminch Town, Southern Nations, Nationalities and Peoples of Ethiopia regional state, South West Ethiopia.

Shecha Health Center is found in Arbaminch Town Administration which will be established in 1961 as a clinic and Upgraded to Health Centre in 2004. Currently the health center serving more than 31,434 populations. Among this, 15,654 were male and 15,780 were female. Shecha Health Centre offers a variety of service delivery units and clinics, including an emergency room, a unit for children under five, an adult outpatient unit, a unit for maternity and child health, a unit for young people, a laboratory unit, a pharmacy unit, a central medical store, an ART clinic, and a TB clinic.

### Study Design

This Therapeutic Efficacy study is a prospective evaluation of clinical and parasitological responses to directly observed treatment for uncomplicated vivax malaria (51,52). People with uncomplicated plasmodium vivax malaria who meet the study inclusion criteria will be enrolled and treated on site with Chloroquine plus Primaquine for *p.vivax* infection and monitored up to 42 days.

The follow-up will consist of a fixed schedule of check-up visits and corresponding clinical and laboratory examinations. On the basis of the results of these assessments, the patients will be classified as having therapeutic failure (early or late) or an adequate response.

The proportion of patients experiencing therapeutic failure during the follow-up period will be used to estimate the efficacy of the study drugs. Molecular analyses will be used to distinguish between a true recrudescence due to treatment failure and episodes of reinfection as well as determine polymorphisms of known resistance markers. In addition, drug level testing may be conducted depending on the availability of resources. .

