#### **Patient Discontinuation or Protocol Violation**

Patients meeting any of the following criteria will be withdrawn:

- Withdrawal of consent
- Failure to complete the treatment
  - Vomiting both initial and replacement doses at any single time in the treatment (i.e. If the patient vomits both attempts to administer the morning dose that would

- require withdrawal; however, vomiting the initial morning dose but not the morning replacement dose would not require withdrawal), persistent vomiting
- Severe side-effects necessitating hospitalization
  - Progression to severe malaria
  - Failure to attend the scheduled visit during the first 3 days
  - Enrolment violation
    - Severe malaria on day 0
    - Erroneous inclusion of a patient outside of the inclusion/exclusion criteria
  - Voluntary protocol violation: Antimalarial (or antibiotics with antimalarial activity) treatment administered by a third party or self-medication with antimalarial (or antibiotics with antimalarial activity) assessed by asking participants or their caretaker at follow-up visits (Annex VI)
  - Involuntary protocol violation
    - Occurrence during the follow-up of concomitant disease that would interfere with a clear classification of the treatment outcome
    - Detection of a mono-infection with another malaria species during follow-up
    - Misclassification of a patient due to a laboratory error (parasitemia) leading to the administration of the rescue treatment

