## Statistical Analysis

Every data from recruited patients will be imported into the WHO Excel sheet (double entry) which is designed for analysis of therapeutic efficacy study data. Data will be also entered in to IBM SPSS (version-26) software to calculate descriptive statistics (mean, median, standard deviations, range). Independent sample t-test will be used to compare baseline temperature and parasitemia between children and adults; mean blood Hb level at D0, D14, D28 and D42 between patients with parasitemia  $\geq 10,000$  and  $< 10,000/\mu\text{l}$  blood. Non-parametric (median) test for independent sample will be used to compare D1 parasitemia between children and adults and paired sample t-test will be used to compare mean Hb level between D0 and D14, D0 and D28, D14 and D28, D0 and D42, D28 and D42. All comparisons will be performed at 95% CI and significance level of 0.05.

Kaplan Meier (K-M) survival analysis and per protocol (PP) analysis will be used for estimation of primary outcomes and PP analysis method will be used to analyze secondary outcomes. The K-M survival analysis method provides better approximation of cure rates as it incorporates probabilities for censored data (incomplete observations due to LFU and withdrawals) in to the analysis. The WHO excel sheet is especially designed for estimation of cure rate based on K-M survival estimator analysis method.

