***Late Parasitological Failure (LPF)***

- Presence of parasitemia on any day between day 7 and day 42 and axillary temperature  $< 37.5$  °C in patients who did not previously meet any of the criteria of Early Treatment Failure or Late Clinical Failure.

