### Treatment Failure (TF)

Clinical deterioration due to *P. vivax* illness requiring hospitalization in the presence of parasitemia

Presence of parasitemia and axillary temperature  $\geq 37.5^{\circ}\text{C}$  on any day between day 3 and day 28/42

Presence of parasitemia on any day between day 7 and day 28/42, irrespective of clinical condition

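### The molecular step allows only recrudescence or reinfection, so any P. vivax relapse is mislabelled, and no rule says what the label does to the patient's outcome

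*Combined protocol and SAP*

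**What the plan says.** **Molecular step.** Study Design first ties efficacy to failures of any kind: "The proportion of patients experiencing therapeutic failure during the follow-up period will be used to estimate the efficacy of the study drugs". It then adds: "Molecular analyses will be used to distinguish between a true recrudescence due to treatment failure and episodes of reinfection". Resistance-marker polymorphisms and, if resources allow, drug levels are also mentioned. Under Laboratory Examination, blood spots are planned at enrolment, on days 3 and 7, and at failure.

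**Relapse.** The Background describes the combination as "highly effective in clearing the parasites from the blood and preventing" relapses (the last word follows a page break). No later section mentions relapse.

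**Failure definitions.** In Annex 4, late parasitological failure is "Presence of parasitemia on any day between day 7 and day 42 and axillary temperature" below 37.5 °C, and the separate P. vivax list has "Presence of parasitemia on any day between day 7 and day 28/42, irrespective of clinical condition". Neither carries a genotype condition, nor does late clinical failure.

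**Analysis.** Statistical Analysis states: "Kaplan Meier (K-M) survival analysis and per protocol (PP) analysis will be used for estimation of primary outcomes". It describes "censored data (incomplete observations due to LFU and withdrawals" and names neither a genotype-corrected nor an uncorrected estimate. Patient Discontinuation or Protocol Violation lists one kind of later infection as a violation: "Detection of a mono-infection with another malaria species during follow-up".

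**What is being evaluated.** Dependent Variables names the efficacy of CQ+PQ. Classification of Treatment Outcomes, in its statement of the primary outcome, names chloroquine alone for P. vivax.

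**The concern.** Primaquine is in the regimen, on the protocol's own account, because the combination is meant to prevent relapse. A recurrence during follow-up could therefore be a recrudescence, a reinfection or a relapse, and the molecular step has a place for only the first two.

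Two things are at stake. The first is attribution. A relapse that matches the day-0 genotype would be labelled recrudescence, the label that Study Design links to treatment failure. The Statement of the Problem sets out to monitor resistant strains, and the primary-outcome wording names chloroquine alone, so a failure of relapse prevention could be reported as chloroquine failure.

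The second is the estimate. A relapse that differs from day 0 would be labelled reinfection. The plan does not say whether that label changes the patient's outcome.

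**Working it through.** **1. The plan's own figure.** Sample Size Determination uses p = 0.05, d = 0.05 and z = 1.96: n = 1.96² × 0.05 × 0.95 / 0.05² = 72.99, so 73. With the 20% allowance, 73 × 1.2 = 87.6, so 88. Both reproduce. Neither depends on the molecular step; they supply only the scale for the illustrations below.

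**2. What the rule does to a relapse.** The documents describe no genotyping method or comparison rule. I assume that the recurrence sample is compared with the enrolment sample, and that a match or mismatch does not show whether the parasites came from surviving blood stages, the liver or a new bite.

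- Relapse matching day 0: labelled recrudescence. Wrong.
- Relapse differing from day 0: labelled reinfection. Wrong.

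No third label exists, so mislabelling follows from the rule itself. The documents give no relapse rate, but they do not allow it to be taken as zero. Annex 9 schedules study drug on days 0 to 2 only (with a conditional entry for any other day), whereas Annex 5 gives primaquine for 14 days, or weekly for 8 weeks in G6PD deficiency. Eight weekly doses starting on day 0 would end on day 7 × 7 = 49, after the 42-day follow-up.

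**3. What the text does with the outcome.**

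- Annex 4: parasitaemia in the stated windows is failure, with no genotype condition.
- Statistical Analysis: censoring is attributed to loss to follow-up and withdrawal only.
- Protocol violations: infection with another species is listed; P. vivax reinfection is not.
- Study Design: treatment failure is attached to recrudescence in the molecular sentence, but to all therapeutic failure in the sentence before it.

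The literal reading keeps a detected relapse as failure. No section states the link from genotype to outcome in either direction.

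**4. Size if reinfections were dropped.** Expected recurrences: 0.05 × 73 = 3.65, about 4. The split between sources is assumed; intervals are exact 95%.

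- All 4 counted: 4/73 = 5.5% (1.5 to 13.4).
- 2 dropped from numerator and denominator: 2/71 = 2.8% (0.3 to 9.8).
- All 4 dropped: 0/69 = 0%.
- All 4 same-genotype relapses: 4/73 = 5.5% labelled recrudescence, when blood-stage failure would be 0%.

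Under Kaplan-Meier the 2 would be censored at recurrence rather than removed. With no other losses, the estimate is 1 − (72/73)(71/72) = 2/73 = 2.7% if both remaining failures come first, and 1 − (70/71)(69/70) = 2/71 = 2.8% if both come last.

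**5. Size if relapses come on top of the planned 5%.** Assume 4 recrudescences, no reinfections and a varying number of relapses among 73 patients.

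| Assumed relapses | Counted as failure | Removed | Difference (points) |
|---|---|---|---|
| 0 | 4/73 = 5.5% (1.5 to 13.4) | 4/73 = 5.5% (1.5 to 13.4) | 0 |
| 2 | 6/73 = 8.2% (3.1 to 17.0) | 4/71 = 5.6% (1.6 to 13.8) | 2.6 |
| 4 | 8/73 = 11.0% (4.9 to 20.5) | 4/69 = 5.8% (1.6 to 14.2) | 5.2 |
| 7 | 11/73 = 15.1% (7.8 to 25.4) | 4/66 = 6.1% (1.7 to 14.8) | 9.0 |

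The planned margin is 5 points.

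**The case against.** The strongest reply is that the plan already does the right thing. Annex 4 ignores genotype, the censoring reasons omit it, and no corrected estimate is named, so a detected relapse counts as failure. Since the dependent variable is efficacy of the combination, that is a correct classification. Counting all recurrences as failure then largely restates Annex 4.

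This stands as far as the estimate goes. A reader might infer from Study Design that relapses will be taken out of failure and efficacy overstated. The documents do not support that, because no section excludes, censors or reclassifies a P. vivax recurrence on its genotype. The rules built into the WHO spreadsheet are not in the documents, so removal is neither shown nor excluded.

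A reader might also infer that the trial will claim chloroquine resistance from matching genotypes. That goes too far as well: resistance markers, and possibly drug levels, are planned, so such a claim need not rest on matching alone.

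The figures are also open to challenge. The 5% in the sample-size section is expected failure with no split by source, so the illustrations show what is arithmetically possible and are not evidence of bias.

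The reply does not rescue the two-way sort. Counting a relapse correctly as failure of CQ+PQ does not stop the molecular step from giving it a wrong source.

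**Conclusion.** The point holds as a faulty stated rule in the molecular step, together with a missing link from its result to the outcome. For a regimen that the protocol credits with preventing relapse, a sort without a relapse or indeterminate category mislabels every relapse it meets. The likely harm is misattribution: a failure of relapse prevention reported as recrudescence and read as chloroquine failure.

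An effect on the primary estimate is possible but not documented. If reinfections were dropped, failure could move from 5.5% to 2.8% or 0% with 4 recurrences in 73, or by 2.6 to 9.0 points if 2 to 7 relapses came on top of 4 recrudescences. All of this rests on assumed numbers of relapses, an assumed split by genotype and an exclusion that the plan does not state. It should be settled before analysis; Annex 4 supplies a usable default.

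**What to change.** - In Study Design, replace the recrudescence-versus-reinfection sort with same or different genotype from day 0, and state that neither result identifies or rules out relapse.
- In Statistical Analysis, confirm that the primary Kaplan-Meier and per-protocol estimates use the Annex 4 definitions without genotype correction, so that all P. vivax recurrences to day 42 count as failure of CQ+PQ. Report genotype descriptively.
- State that failure by itself is not evidence of chloroquine resistance.
- Reconcile Study Design, Dependent Variables, Classification of Treatment Outcomes, Statistical Analysis and Annex 4 on this point, including whether the primary outcome concerns chloroquine or the combination.

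The cost is wording; samples and assays are unchanged. The downside is that true reinfections stay counted as failures, so the failure rate may look slightly less favourable than a corrected one.

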## Population

### Source Population

All Malaria Patients who visit Shecha Health Centre during the study period.

### Study Population

Confirmed mono *p.vivax* malaria patients visiting Shecha Health Centre during the study period who fulfilled the inclusion criteria set by the WHO protocol for the assessment of the therapeutic efficacy of Chloroquine plus Primaquine.

### Eligibility Criteria

#### Inclusion Criteria

- ♣ Age > 6 months
- ♣ Slide confirmed infection with *P. vivax* with > 250 asexual forms/ $\mu$ l
- ♣ Lives within 5 km of the enrolling health facility
- ♣ Weight  $\geq$  5.0 kg
- ♣ Ability to swallow oral medication
- ♣ Ability and willingness to comply with the protocol for the duration of the study and to comply with the study visit schedule
- ♣ Informed consent from patient or from a parent or guardian in the case of children

#### Exclusion Criteria

- ♣ Severe malaria with complication sign and symptoms (see Annex I)
- ♣ Signs or symptoms of severe malnutrition, defined as weight-for-age  $\leq$  3 standard deviations below the mean, symmetrical edema involving at least the feet, or mid-upper arm circumference <100 cm for children less than five years of age (NCHS/WHO normalized reference values; see Annex I)
- ♣ Mixed plasmodium infection
- ♣ Severe anemia, defined as hemoglobin (Hb) < 8 g/dl

- ♣ Presence of febrile conditions caused by diseases other than malaria (e.g. measles, acute lower respiratory tract infection, severe diarrhea with dehydration)
- ♣ Serious or chronic medical condition (e.g. cardiac, renal, hepatic diseases, sickle cell disease, HIV/AIDS)
- ♣ Positive pregnancy test or breastfeeding
- ♣ Unable or unwilling to take contraceptives for women of child-bearing age
- ♣ Children weighing less than 5 kilograms
- ♣ History of hypersensitivity reaction to any medication tested or used as an alternative treatment
- ♣ Participants with history of prolonged QT conditions
- ♣ Taking regular medication, which may interfere with antimalarial pharmacokinetics or efficacy (see Annex VII)?

## Sample Size Determination and Sampling Technique

### Sample Size Determination

The sample size will be determined according to the WHO (2009) protocol(11); by using the single population proportion formula and calculated assuming 5% margin of error, 95% confidence interval (CI), and treatment failure of 5% and 20% loss to follow-up rate. Accordingly, a minimum of 73 patients will be enrolled.

$$\text{Sample size (n)} = \frac{[(Z \alpha/2)^2 p(1-p)]}{d^2}$$

$$\frac{(1.96)^2 0.05 (1-0.05)}{(0.05)^2} = 73$$

Assuming an additional 20% loss to follow-up rate and withdrawal of consent (15 patients) during the study, at least 88 (73 + 15) patients will be required to bring about a representative sample size.  $n = (1+0.2) 73 = 88$  Where, n= sample size

P=Expected treatment failure (5%)

Z=confidence interval (95%)

d=margin of error (5%)

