### **Operational Definitions and Definition of Terms**

#### **Loss to Follow-Up**

Loss to follow-up occurs when, despite all reasonable efforts, an enrolled patient does not attend the scheduled visits and cannot be found. No treatment outcome will be assigned to these patients. Every effort must be made to schedule a follow-up visit for patients who fail to return to the study site, especially during but also after administration of the study drug. These patients will be classified as lost to follow-up and censored or excluded from the analysis. Patients who are lost to follow-up but who subsequently return to the study site before day 42 will not be turned away and will be encouraged to return for check-up visits. The principal investigator will decide whether the patient is to be classified as lost to follow-up based on his or her history or is to be maintained for the analysis.

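### The enrolment target of 88 tolerates a 17% loss to follow-up, not the 20% that the plan states (minor)

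*Combined protocol and SAP*

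**What the plan says.** Under Sample Size Determination, the number is "calculated assuming 5% margin of error, 95% confidence interval (CI), and treatment failure of 5% and 20% loss to follow-up rate". The section puts these inputs into the normal-approximation formula for one proportion, obtains 73, and states: "Accordingly, a minimum of 73 patients will be enrolled".

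It then makes the allowance for drop-out: "Assuming an additional 20% loss to follow-up rate and withdrawal of consent (15 patients) during the study". The 15 patients are added to 73, and the same step is also written as 1.2 times 73. Both give 88, which the section sets as the number required.

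Three other sections bear on how much the loss matters:

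- Study Design makes the failure proportion the efficacy measure: "The proportion of patients experiencing therapeutic failure during the follow-up period will be used to estimate the efficacy of the study drugs".
- Loss to Follow-Up says of patients who cannot be found: "These patients will be classified as lost to follow-up and censored or excluded from the analysis".
- Statistical Analysis names two estimators: "Kaplan Meier (K-M) survival analysis and per protocol (PP) analysis will be used for estimation of primary outcomes".

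**The concern.** The formula fixes how many patients must contribute an outcome for the margin to be 5 points. To keep that number after a given fraction of enrolled patients is lost, it must be divided by one minus the fraction. Multiplying by one plus the fraction gives too few. The plan multiplies, so at its own stated loss rate it does not keep its own 73.

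Precision is the only justification given for the sample size, so the figure should be right on its own terms. The label on the 73 is also loose. It is the number needed for analysis, but the text calls it a minimum to be enrolled and a few lines later requires at least 88.

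**Working it through.** **Inputs, all from Sample Size Determination:** failure proportion p = 0.05; margin d = 0.05; z = 1.96; loss 20%; 15 patients added.

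**1. The plan's own figures.**
- Base: 1.96² × 0.05 × 0.95 / 0.05² = 72.99, so 73. Reproduced.
- Allowance: 0.20 × 73 = 14.6, so 15, and 73 + 15 = 88. Equivalently, 73 × 1.2 = 87.6, so 88. Reproduced.

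**2. The loss that 88 tolerates.** If 88 are enrolled and 73 must remain, 15 may be lost: 15/88 = 17.0%. The 15 is about 20% of 73, not of 88.

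**3. What remains at the stated 20%.** 88 × 0.80 = 70.4, so about 70.

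**4. Effect on the planning margin,** 1.96 × √(0.05 × 0.95 / n):

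| Evaluable n | Margin (percentage points) |
|---|---|
| 73 | 5.00 |
| 70 | 5.11 |

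**5. Enrolment that would keep 73 at 20% loss.** 73 / (1 − 0.20) = 91.25, so 92, which is 4 more than 88. Then 92 × 0.80 = 73.6 evaluable, with a margin of 4.98 points.

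**6. Which estimate is affected.** Patients lost before an outcome is assigned drop out of the per-protocol denominator, so steps 3 and 4 apply there directly. In the Kaplan-Meier estimate they count up to the day of censoring, so the effective loss is smaller. How much smaller depends on when patients are lost, which the documents do not say.

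**7. Expected failures, for the secondary suggestion.** 0.05 × 73 = 3.65 and 0.05 × 70 = 3.5, so fewer than 4. With 3 failures in 70, the 95% limits are:

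| Method | Lower (%) | Upper (%) |
|---|---|---|
| Normal approximation | −0.5 | 9.0 |
| Wilson | 1.5 | 11.9 |
| Exact | 0.9 | 12.0 |

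**The case against.** The best defence is that the plan shows its convention openly. It speaks of an additional 20%, gives the 15 patients, and writes out the multiplication, so the sum agrees with its own formula. The effect is about 0.1 point on a margin given as a whole percentage. One of the two primary estimators also uses the follow-up of patients who are lost. All of this stands, and it is why the point is minor. It does not remove the mismatch, because the section also calls the same 20% the loss to follow-up rate, and 88 does not leave 73 at that rate.

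A reader might infer two stronger points, and the documents support neither.

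- **That recruitment could stop at 73.** The wording permits this if read alone, but the lines that follow require at least 88. It is a labelling fault.
- **That the reported confidence interval will cover too rarely.** At a true failure rate of 5%, a nominal 95% normal-approximation interval covers 88.2% with 73 patients and 86.3% with 70. But a planning formula does not commit the analysis to that interval, and no section says it will be reported. The analysis section says only "All comparisons will be performed at 95% CI and significance level of 0.05", and of the cure rate "The WHO excel sheet is especially designed for estimation of cure rate based on K-M survival estimator analysis method". The documents do not show which interval that sheet produces. Coverage also swings with the true rate: with 73 patients it is 94.7% at 4% and 93.4% at 6%, although only 77.1% at 2%. The figure at 5% is therefore not a stable property of the design. What remains is a missing detail.

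**Conclusion.** The stated allowance and the stated loss rate do not agree. Enrolling 88 protects the required 73 against a loss of 17.0%. At 20%, about 70 remain and the planning margin is 5.1 points, against the planned 5.0. The consequence is minor: a shortfall of 4 enrolled patients and no change to any design decision.

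This rests on three assumptions. The 73 is the number of evaluable patients, as the added allowance implies. The 20% is a fraction of those enrolled, which is the usual meaning of a loss rate. It also covers every reason for having no outcome; the protocol lists further grounds for withdrawal, and if these come on top, the per-protocol number falls further by an amount the documents do not give.

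The choice of interval is a suggestion only, because the documents do not say which will be used.

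**What to change.** **Correction.** Keep 88 and replace the sentence that calls 73 a minimum for enrolment with, for example:

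> 73 evaluable patients are required. 88 will be enrolled, which tolerates a loss of up to 17%. At 20% loss about 70 would be evaluable (margin 5.1 points).

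This is a text edit and costs nothing in recruitment. If the 20% allowance is to be kept in full, write 73/(1 − 0.20) = 92 instead, at a cost of 4 more patients. Either way, label one number as evaluable and the other as enrolled.

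**Optional.** In Statistical Analysis, state that the per-protocol failure proportion will be reported with an exact or Wilson 95% interval, since fewer than 4 failures are expected. If the WHO Excel sheet does not offer one, a short calculation outside it is enough.
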